A recent genome wide association study conducted in our laboratory revealed two significant single nucleotide polymorphisms (SNP) in a large cohort of pediatric patients with ALL. One SNP, rs10454966 is part of the COCH gene and is associated with progressive hearing loss and vestibular imbalance^{31,32}. Two studies of pediatric cancer survivors found hearing loss to be more prevalent in survivors as compared to controls^{26,33},

suggesting the COCH gene SNP as a potential indicator of future hearing loss. The second SNP, rs7963521 is associated with plasma/serum levels of Chemerin³⁴. Chemerin, a protein, is processed from its preprochemerin form and can be involved in angiogenesis³⁵, adipogenesis³⁶, osteoblastogenesis³⁷ or inflammatory processes³⁸⁻⁴⁰ pathways affected by chemotherapy. Recently, one study identified chemerin levels as an independent predictor for 5-year mortality in patients with gastric cancer⁴¹. Given our preliminary findings it is important to investigate further into *Chemerin as a novel target for understanding neuropathy, a potential biomarker for dosing vincristine during treatment and as an indicator of long-term consequences of treatment.*

Our research team has discovered two other potential biomarkers, Platelet Derived Growth Factor BB (PDGF-BB) and Interleukin 13 (IL-13)⁴². Utilizing blood samples from pediatric ALL patients, [name] discovered PDGF-BB levels were negatively associated with worse peripheral neuropathy, while IL-13 was positively associated with it. The study proposed in this application is going to verify the preliminary data found for these biomarkers.

Following peripheral nerve injury many neurotrophins and proteins are expressed to aid in the nerve repair process. In addition to the biomarkers found in our research study, PDGF-BB and IL-13, we will also measure three markers of neuronal repair: nerve growth factor (NGF), synapsin 1 (SNAP1), and growth associated protein 43 (GAP43). Molteni and colleagues (2004) demonstrated in a rodent model of nerve crush injury that rodents which exercised also displayed enhanced regrowth of axons that were associated with increased levels of NGF, GAP43, and SNAP1¹¹. There is also extensive evidence on the positive effects of exercise on sensory nerves and neuropathic pain. Cooper et al (2016) recently published a review on this topic discussing the mechanisms underlying exercise and explaining the role of the NGF, SNAP1, and GAP43 in the repair process¹⁰.

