Exercise: EX increases oxygen to all organ systems, including the nervous system ¹⁰. Emerging data support the notion that EX protects against chemotherapy-induced peripheral neuropathy (CIPN) and may help repair damaged nerves after CIPN develops. Exact EX prescriptions have not yet been developed, but the more hours spent in moderate-to-vigorous activity, the less peripheral neuropathy experienced⁶⁸.

Oxygenation: The increase in oxygen which occurs during exercise (both aerobic and resistance) has been shown to increase NGF⁶⁹, SNAP1⁷⁰, and GAP 43¹¹ in rodent models of exercise. In addition, oxygenation enhances the pathway that increases Myelin Basic Protein (MBP), thus helping maintain myelin homeostasis⁷¹. Myelin is important for nerve conduction and is targeted during chemotherapy⁷², thus maintaining healthy myelin sheaths around the axons is necessary to minimize neuropathy.

Biomarkers: We have selected three key factors, NGF, SNAP1 and GAP 43 known to have a role in neuronal repair¹⁰ and one involved in myelination disease, PDGF-BB⁷³ to investigate in the current study. These factors should increase to compensate for any neuronal damage inflicted by the chemotherapy. In addition, we have data suggesting that the cytokine, IL-13 is also associated with VIPN⁴². In this instance, the higher the IL-13 plasma levels the worse the neuropathy, therefore we expect exercise to decrease this cytokine.

Quality of Life: Childhood and AYA cancer has a considerable negative effect on a child's physical wellbeing due to chemotherapy, radiation and the resultant side effects of each. Improving the symptoms that result from cancer treatment (e.g., VIPN) and decreasing symptom burden is related to improved quality of life in this population. Further, exercise has been shown to improve both muscle weakness and low cardiorespiratory fitness⁷⁴ for childhood and AYA cancer survivors, which may also improve their quality of life.

F. ELIGIBILITY CRITERIA

F.1 Inclusion criteria

Participants will be eligible for this study if they are:

- (1) age \geq 5 and \leq 25 years, (Riley Hematology/Oncology division accepts patients through age 25)
- (2) have been initially diagnosed with acute lymphoblastic leukemia (ALL), or lymphoblastic lymphoma (LL) and may also be a relapsed diagnosis,
- (3) will undergo the standard of care treatment for ALL or LL with vincristine.
- (4) will have a TNS-PV score of 3 or greater at week 6

F.2 Exclusion Criteria

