Each EX chapter will EX muscle groups in the following order: 1) lower body EXs, 2) upper body EXs and, 3) core strengthening EXs. Each muscle group will follow the order of largest muscle group to smallest muscle group. The EX chapters will follow a Recovery Program format in which larger muscle groups are exercised before smaller muscle groups to prevent fatigue and optimize adherence. The Whole-Body Recovery Program will ensure that the weakest or the most deconditioned muscle groups will have the chance to become reconditioned as all muscle groups (agonist and antagonist) are utilized. Engaging all major muscle groups simultaneously will strengthen all joints involved.

I.4 Demographic and Clinical Data Collection/Measures

Demographic and Medical Information

Demographic data obtained at time of consent will include race, age, gender, ethnicity, and pre-diagnosis exercise level prior to diagnosis. We will use age and baseline exercise level as covariates. Exercise levels will be determined by the exercise therapist based on the recommendations from the World Health Organization for children 5-17 which is seven hours per week of aerobic activity⁷⁶. The therapist will ask the child about their pre-diagnosis activity level and record it on the physical assessment form. The categories will be as follows: below recommended level of activity, at recommended level of activity, and above recommended level of activity. All medical information (dates and doses of vincristine) will be collected by the study coordinator from the subject's medical records.

Vincristine-induced Peripheral Neuropathy

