Based on our conceptual model, we will also examine associations between change scores for predictors and change scores for primary and secondary outcomes. For example, we will estimate Pearson correlations between changes in self-efficacy, outcome expectations, support, neuropathy, pain, and quality of life.

We will also examine whether or not the circulating protein biomarkers at T1 are associated with VIPN severity at T1 using Spearman correlations and whether initial or dynamic levels of the circulating biomarkers are predictive of intervention efficacy. The associations between VIPN and the genetic and circulating biomarkers will be analyzed through generalized linear mixed models, which includes a random subject effect to account for the correlation of observations from the same subject.

J.3 Missing Data

We expect minimal dropout at 14 weeks (primary endpoint for the proposed trial) and have inflated the sample size to account for the expected 15% attrition, so we anticipate it will not create any substantial bias in the results. To aid in future studies, we will compare baseline characteristics among those who complete the study and those who do not to determine if there are any characteristics associated with study completion.

K. RISKS OF PARTICIPATION AND PROTECTION OF HUMAN SUBJECTS

K.1 Risks

Possible risks to participation in this study are breach of confidentiality, physical distress or emotional distress due to study participation. All contact with the participant will be documented beginning at the consent process through completion of the study. All documentation will be reviewed regularly. Any events that might indicate increased participant physical distress or emotional distress will be promptly brought to the attention of the PI and reported to the IRB and DSMC per reporting guidelines listed below. We will promptly report to the IRB any instances of consent withdrawal due to distress. The IRB will be informed at least annually of our data and safety monitoring, summary of participant status, and any changes in the risk of the study.

Prevention of injuries have been addressed through 1) video design, 2) safety reminders during videos and fitness assessment and 3) muscle soreness. The video design is based on a specific gradual workout design to ensure safety for the most deconditioned patients. The study has incorporated beginner (seated or bed), intermediate (bridge between beginner and advanced) and advanced EX chapters.

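### The baseline biomarker–VIPN correlations are planned without the two covariates the protocol names, so activity may confound them; adjusted values should be added beside the unadjusted ones

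*Combined protocol and SAP*

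**What the plan says.** Section J.2 will test whether "circulating protein biomarkers at T1 are associated with VIPN severity at T1 using Spearman correlations". No covariate is mentioned, and a bivariate Spearman correlation cannot hold one. The same paragraph continues: "The associations between VIPN and the genetic and circulating biomarkers will be analyzed through generalized linear mixed models". The only model term it gives for these is a random effect for subject. Those models could carry covariates, but none is named.

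Section I.4 states: "We will use age and baseline exercise level as covariates". The exercise variable is the level before diagnosis, as reported to the therapist, in three categories: "below recommended level of activity, at recommended level of activity, and above recommended level of activity". In J.2 the two covariates appear only in the repeated measures ANOVA of change from T1 to T2.

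On theory, Section E says that "the more hours spent in moderate-to-vigorous activity, the less peripheral neuropathy experienced". It also says "The increase in oxygen which occurs during exercise (both aerobic and resistance) has been shown to increase NGF", along with SNAP1 and GAP 43; that sentence goes on to limit the evidence to rodent models. Section E expects exercise to lower IL-13. Section B says exercise lowers chemerin, although Hypothesis 3 of Aim 2 lists chemerin with the markers expected to rise. The same hypothesis expects PDGF-BB to rise.

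Section C reports preliminary data in which worse neuropathy went with lower PDGF-BB and higher IL-13, and adds: "The study proposed in this application is going to verify the preliminary data found for these biomarkers".

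**The concern.** A more active patient could have both a different marker level and a lower TNS-PV, with no direct relation between the two. An unadjusted correlation cannot separate that from a real marker–neuropathy link.

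This matters most for PDGF-BB and IL-13. If activity raises PDGF-BB, lowers IL-13 and lowers neuropathy, activity alone produces the two signs found in the preliminary data. The study could then appear to verify those data when the marker only tracks how active the patient is, and such a marker could be carried into later work.

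The plan already collects two covariates that bear on this and names them as covariates, but does not bring them into these analyses.

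**Working it through.** **Does other text in the plan close the gap?** The T1 question is assigned to Spearman correlations. The mixed models name a random subject effect only. The ANOVA that carries the covariates concerns change in outcomes, not marker–VIPN association. I.4 does not say which analyses its sentence covers. The gap therefore stands as an omission.

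**The plan's own figures.** H.1 gives no figure for the correlation analysis. Its paired t-test figures reproduce: n = 34 with a .5 SD difference gives power .808; a 2-point change with SD of the difference 3.66 × √(2 × (1 − .4)) = 4.01 gives .806; and 34 / (1 − .15) = 40. None of these depends on this point.

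**How large could the confounding be?** The documents give no correlation of activity with any marker or with TNS-PV, so r below is an assumption. Suppose activity correlates +r with the marker and −r with VIPN, with no direct link. The induced correlation then has size r × r. The rejection rate at n = 40 was obtained by simulation: 6,000 runs per setting, a three-level activity factor, and age unrelated to either variable. It was checked with the Fisher z approximation, SE = 1/√37.

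| Assumed r | r × r | Mean simulated rho | Plain Spearman rejects (simulation) | Fisher z check |
|---|---|---|---|---|
| .2 | .04 | −.04 | 5% | – |
| .3 | .09 | −.09 | 9% | 8.5% |
| .4 | .16 | −.15 | 16% | 16.6% |
| .5 | .25 | −.24 | 34% | 34.2% |

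In the same runs the rank-based partial correlation, adjusted for the three activity levels and age, rejected in 4.5% to 5.2%. That is a best case, because the adjusted factor was itself the confounder.

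**How much would the recorded covariate remove?** Suppose activity around T1 is the confounder, with r = .5, and the pre-diagnosis category correlates c with it (also assumed). The category then correlates .5c with each variable, and the size of the partial correlation is

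(.25 − .25c²) / (1 − .25c²).

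- c = .3: .2275 / .9775 = .23
- c = .5: .1875 / .9375 = .20
- c = .7: .1275 / .8775 = .15

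With three adjustment terms (SE = 1/√34) the test still rejects in about 28%, 22% and 14%, against 34% unadjusted. Adjustment helps but does not remove the bias.

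**What does adjustment cost?** Two indicators for exercise level and one term for age use three degrees of freedom. The critical |rho| is t/√(df + t²):

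- df = 38: 2.0244 / √(38 + 4.098) = .312
- df = 35: 2.0301 / √(35 + 4.121) = .325

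The rho detectable at 80% power, with the Spearman variance factor 1.06, is tanh[(1.960 + .842) × √1.06 / √(n − 3 − k)]:

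- k = 0: .44
- k = 3: .46

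**The case against.** The strongest reply is that a Spearman correlation validly answers the question J.2 asks, namely whether marker and severity are associated. Section D wants markers that predict severity, and marginal association is relevant to that. On this view a rejection at a true marginal correlation of .25 is correct, and is false only if read as evidence of a direct link. This stands, and is why the unadjusted values should be kept.

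Second, a reader might infer that activity is an established common cause and that the planned correlations will therefore be spurious. The documents do not support that. Their theory also fits a chain in which exercise changes the markers and the markers aid nerve repair. In a pure chain, exercise does not confound the marker–VIPN association. Section E also expects repair factors to rise in response to nerve damage, so confounding could mask an association as well as create one. The evidence for NGF, SNAP1 and GAP 43 is from rodents.

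Third, a reader might infer that J.2 contradicts I.4. It does not: I.4 ties its covariates to no particular analysis, and the ANOVA uses them.

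Fourth, the covariate is not current activity. It is a recalled pre-diagnosis category, while T1 falls during vincristine treatment. This stands and limits the gain, as shown above. In its favour, the category describes a time before vincristine, so it cannot be a consequence of VIPN.

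Fifth, the documents link age to neither marker level nor TNS-PV. The case for including age rests on its being a named covariate in a sample aged 5 to 25, not on demonstrated confounding.

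**Conclusion.** The point holds in a limited form. The T1 marker–VIPN analysis is unadjusted, the related mixed models name no covariate, and the protocol's own theory makes confounding by activity plausible. Its size is unknown. Under assumed correlations of .2 to .5 with both variables and no direct link, the rejection rate at n = 40 runs from about 5% (no effect) to 34%. At .3 or below the effect is nil to small, and nothing in the documents favours the upper end. Adjustment for the recorded category would remove only part of any bias.

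This analysis is not among the listed hypotheses of either aim, and J.2 adds it as a further examination in a 40-patient single-arm feasibility study. The point is a cheap improvement to an exploratory analysis. It is not an error that affects the feasibility outcome, the TNS-PV change analysis or the sample size.

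**What to change.** In J.2:

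- Keep the unadjusted T1 Spearman correlations and label them descriptive marginal associations. They remain comparable with the preliminary data.
- Report beside them rank-based partial Spearman correlations adjusted for age and baseline exercise level, with exercise level entered as its three categories.
- Enter the same two covariates as fixed effects in the VIPN–biomarker mixed models.
- State that the exercise covariate describes activity before diagnosis, so that some confounding by activity around T1 may remain.

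This takes a few sentences in J.2 and no new data, since I.4 already provides for both covariates. The statistical cost is the three degrees of freedom shown above, and because the unadjusted result is kept, nothing planned is lost.

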Participants will be ineligible for this study if they have:

- (1) baseline peripheral neuropathy greater than grade 1 (prior to receiving any doses of vincristine),
- (2) evidence of significant liver dysfunction,
- (3) Down's Syndrome,
- (4) pregnancy,
- (5) severe illness or infection,
- (6) current active treatment with erythropoietin,
- (7) administration of vitamin supplements above 100% of the recommended daily allowance

G. PATIENT RECRUITMENT

Potential subjects will be recruited from the Riley Hospital for Children (Riley) and IU North Hospital. Riley medicine doctors are dedicated to the care of pediatric, adolescent and young adults ages 1-25. Study personnel will work with the clinicians in the Riley Department of Hematology Oncology to obtain the names of patients who have diagnoses of acute lymphoblastic leukemia (ALL) or Non- Hodgkin's Lymphoma-lymphoblastic lymphoma (LL) and are planning to undergo vincristine treatment. Patients will be recruited during their first 4 weeks of vincristine treatment.

Potential minor subjects and their parents/legal guardians may be approached by their physician and/or study personnel with information about this study. Patients and their parents/legal guardians who are interested in participating in the study will undergo the informed consent process. Informed consent will be only obtained by trained and authorized study personnel or investigators. Patients and their parents/legal guardians may be given a study flyer with contact information at the time of consent.

After consent, eligibility will be verified by a member of the study team and the patient will be registered (i.e., enrolled) to this study. The original, signed, IRB-approved Informed Consent Document and all regulatory files will be maintained by the Pediatric Clinical Trials Office (PCTO). Applicable regulatory documents must be completed and on file prior to registration of any subjects.

H. RESEARCH DESIGN

This is a multi-center study to test the feasibility of pediatric and AYA patient adherence to a single intervention (exercise: EX) during the consolidation phase of vincristine treatment for Acute Lymphoblastic Leukemia or

Lymphoblastic Leukemia. Fitbit activity tracker data and questionnaires will be used for assessing adherence and feasibility. We will use a pre and post intent-to-treat design. Forty subjects will be recruited and enrollment is expected to last 24 months.

H.1 Sample size justification

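### With every patient exercising, Section J.2 cannot show that a biomarker is predictive of intervention efficacy, only that it is associated with the course of neuropathy

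*Combined protocol and SAP*

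**What the plan says.** Section H describes a study of "patient adherence to a single intervention (exercise: EX) during the consolidation phase" and adds: "We will use a pre and post intent-to-treat design". No comparator is described. Section F.1 requires that a patient "will have a TNS-PV score of 3 or greater at week 6".

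Section J.2 contains two linked biomarker analyses. The first asks whether "circulating protein biomarkers at T1 are associated with VIPN severity at T1 using Spearman correlations". The second asks "whether initial or dynamic levels of the circulating biomarkers are predictive of intervention efficacy". The method sentence that follows is a generalized linear mixed model for the association of VIPN with genetic and circulating markers, with a random subject effect. For this item J.2 gives no definition of efficacy and no exploratory label. The covariates named in J.2, for the repeated measures ANOVA, are age and baseline activity level; T1 TNS-PV is not among them.

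The protocol already links two of the markers to severity. Section C reports that "PDGF-BB levels were negatively associated with worse peripheral neuropathy, while IL-13 was positively associated with it", and Section E says "the higher the IL-13 plasma levels the worse the neuropathy". Section B places the peak of intermediate to severe neuropathy at about week 14. Under Section I.5, blood is taken at week 6 and week 14 only.

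**The concern.** A marker predicts the efficacy of exercise if the benefit of exercise differs by marker level. Seeing that requires the marker's relation to outcome both with and without exercise. Here only the first is observed. A child whose neuropathy would have improved or worsened anyway counts in the same way as one who responded to exercise.

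There is a second, smaller problem. Patients are selected on a high T1 score, and scores at T1 and T2 are only moderately correlated, so change from T1 partly reflects regression to the mean. A marker related to severity can pick up some of that.

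At stake is the biomarker conclusion. IL-13, PDGF-BB or another marker could be carried into the efficacy trial as a marker of exercise response when it only tracks severity or prognosis.

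**Working it through.** **What one arm identifies.** For marker level M, mean change under exercise = natural course(M) + exercise effect(M). The trial estimates the sum. Any slope on M can be assigned wholly to the first term, wholly to the second, or split between them, and no model fitted to these data settles which. With the untreated peak placed at about T2, the natural course cannot be assumed flat.

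**Inputs (Section H.1).** SD 3.66 at both times, T1-T2 correlation r = .4, 34 completers, pilot baseline mean 3.36. Section F.1 gives the threshold of 3. The marker-severity correlation c is not in the documents; I assume .3 to .5.

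**The plan's own figure.** SD of change = 3.66 × √(2 × (1 − .4)) = 4.01. A 2-point change is 2/4.01 = .499 SD. With n = 34, a two-sided paired t-test at .05 has 80.6% power, so the stated 80% reproduces and r = .4 is the plan's working value.

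**Effect of the threshold, assuming normal scores and no exercise effect.**
- Standardized threshold a = (3 − 3.36)/3.66 = −.098.
- λ = φ(a)/(1 − Φ(a)) = .736.
- Remaining fraction of T1 variance, k = 1 + aλ − λ² = .385.
- Mean change in enrolled patients = −(1 − .4) × 3.66 × .736 = −1.6 points.
- Standardized variance of change, V = (1 − r)²k + (1 − r²) = .36 × .385 + .84 = .979.
- Correlation of T1 with improvement (T1 − T2) = (1 − r)√k/√V = .6 × .621/.989 = .376.

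**Case A: the marker follows the observed T1 score.** Its correlation with improvement is c × .376, with c measured in enrolled patients.

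**Case B: the marker follows stable severity**, so it correlates equally with T1 and T2. Its correlation with improvement is −c(1 − r)(1 − k)/√[(1 − c²(1 − k)) × V], with c measured before the threshold is applied. For c = .5: −(.5 × .6 × .615)/√(.846 × .979) = −.20.

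Rejection rates use Fisher's z with n = 34, against a nominal 5%.

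| c | Case A: r | Case A: p < .05 | Case B: r | Case B: p < .05 |
|---|---|---|---|---|
| .3 | +.11 | 10% | −.12 | 10% |
| .4 | +.15 | 13% | −.16 | 14% |
| .5 | +.19 | 18% (18.5% before rounding) | −.20 | 21% |

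The signs are for a marker that rises with severity; they reverse for one that falls with it. The two cases measure c on different bases, so they should be compared for sign and rough size only.

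**Does adjusting for T1 cure it?** In Case A the partial correlation of marker with T2 given T1 is 0, so yes. In Case B it is (c − cr)/√[(1 − c²)(1 − r²)]. For c = .5 that is .30/√(.75 × .84) = .38. For c = .3, .4 and .5 the values are .21, .29 and .38, significant in about 21%, 36% and 59% of trials of 34 with no exercise effect. That is a genuine prognostic association. It says nothing about exercise.

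**Dynamic levels.** A change in marker level is complete only at the week 14 sample, when the outcome is measured. It can accompany the outcome but cannot predict it in time.

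**The case against.** The strongest reply is that this is one secondary clause in a feasibility study. J.2 says the question will be examined, the stated aim is preliminary effect sizes ahead of a fully powered trial, and no eligibility or continuation decision rests on the result. The lack of a control is plain from the design. This limits the weight of the point but does not remove it: the clause names efficacy, carries no caveat, and J.2 does label another analysis, the Fitbit mixed model, as exploratory.

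The regression-to-the-mean argument also needs limits, and these objections stand. J.2 does not say that efficacy means T1 − T2 here, and the method that follows is a mixed model, not a change-score correlation. The marker-severity correlations are assumed. The calculation concerns initial levels only.

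A reader might go further and infer that any severity-related marker will look predictive through regression to the mean alone, in a known direction. The documents do not support that. Cases A and B have opposite signs, and nothing in the protocol says which applies. Even at c = .5, roughly four trials in five show nothing significant. Leaving out the entry threshold gives larger figures (.16 to .27, significant in 15% to 34% of trials), but the threshold is part of the design and they overstate the artefact.

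It is also tempting to think that adjusting for T1 TNS-PV makes the question answerable. Case B shows that it does not; for such a marker the adjusted analysis is significant more often than the change score.

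**Conclusion.** The main point holds without any numerical assumption. With one arm, J.2 can estimate associations between markers and the course of neuropathy, and it cannot attribute them to exercise. Nothing elsewhere in the protocol repairs this.

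The regression-to-the-mean point holds as a possibility: spurious correlations of about .11 to .19 in size, significant in about 10% to 18% of trials of 34 instead of 5%, with the sign undetermined. It rests on reading efficacy as change from T1, on normal scores with the Section H.1 values, and on assumed marker-severity correlations of .3 to .5 in enrolled patients. A planned correlation of .3 instead of .4 makes the artefact somewhat larger; .6 makes it smaller.

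The flaw touches the biomarker claim only. The feasibility and acceptability aim is unaffected.

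**What to change.** In Section J.2, replace the wording on prediction of efficacy with: *associated with TNS-PV at T2, adjusted for T1 TNS-PV (exploratory)*. This also supplies the outcome and the adjustment that the item now lacks. Then add three statements:

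- Such an association may be purely prognostic, even after adjustment for T1.
- Dynamic levels are measured at the same time as the outcome and so do not predict it.
- A predictive claim needs a marker-by-arm comparison in the later controlled trial.

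The relabelling does the main work. The adjusted regression on its own removes the artefact only for a marker tied to the observed T1 score.

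The cost is a few lines of text, with no new patients, visits or samples. The downside is a more modest biomarker claim.

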To address Aim 1, adherence in the intervention group will be measured through a 5 question survey at each treatment and also through start/stop on the Fitbit. Adherence scores will be summarized across time with descriptive statistics (N, mean, SD, median, minimum, and maximum). From start/stop information, the proportion of exercise sessions completed and the proportion of patients which complete at least 50% of the exercise sessions along with associated 95% confidence intervals will be estimated. Additionally, descriptive statistics will be provided for the patient satisfaction survey provided at the end of the study.

To address Aim 2, we will use paired t-tests to examine change from baseline (T1) to 14 weeks (T2). For outcomes which are known to be non-normal such as biomarkers, we will use Wilcoxon-signed rank tests. We plan an intent-to-treat analysis. Even if we do not see significant differences, descriptive statistics including means, SD, and effect sizes (differences in means between the two time points divided by pooled SD) will be reported for outcomes along with 95% confidence intervals. All analysis will include checking of assumptions. Additionally, we will also use repeated measures ANOVA to estimate the contrast of interest (change from baseline at 14 weeks) for primary and secondary outcomes, after adjusting for age and baseline activity level.

For activity outcomes obtained from the FitBit, such as patients' daily number of steps, distance, active minutes, and heart rate, we will start with simple techniques such as paired t-tests or Wilcoxon signed-rank tests to compare the mean change in activity level from baseline (T1: summarized over week 6) to treatment end (T2: summarized over week 13). As an exploratory analysis, we will also use a generalized linear mixed model with appropriate distribution (e.g. Poisson) and link function fit to all weekly outcomes to examine changes over time using time as a continuous variable. We expect to have an abundance of information provided from the Fitbit, thus we will estimate descriptive statistics (N, mean, SD, median, minimum, and maximum) for all outcomes (i.e., number of steps, distance, active minutes, and heart rate) at each week to aid in planning future studies.

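### Aim 2 is labelled intent-to-treat, but its paired tests drop patients without T2 (up to about 6 of 40), and J.3 cites sample-size inflation, which protects only power, as a reason to expect no substantial bias

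*Combined protocol and SAP*

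**What the plan says.** Section H describes the study so: "We will use a pre and post intent-to-treat design". J.2 repeats the label for Aim 2: "We plan an intent-to-treat analysis".

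The Aim 2 tests in J.2 are paired: "we will use paired t-tests to examine change from baseline (T1) to 14 weeks (T2"). For other outcomes: "For outcomes which are known to be non-normal such as biomarkers, we will use Wilcoxon-signed rank tests". J.2 also promises that "effect sizes (differences in means between the two time points divided by pooled SD) will be reported for outcomes along with 95% confidence intervals". In addition it plans "repeated measures ANOVA to estimate the contrast of interest (change from baseline at 14 weeks"), adjusted for age and baseline activity level. It does not say what that model does with a patient who has T1 but no T2.

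H.1 enrols 40 so that at least 34 complete week 14, assuming 15% attrition, and bases power on 34.

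J.3 opens with "We expect minimal dropout at 14 weeks (primary endpoint for the proposed trial") and, in the same sentence, says that the investigators "have inflated the sample size to account for the expected 15% attrition, so we anticipate it will not create any substantial bias in the results". The only further step, in J.1 and J.3, is a baseline comparison of completers with non-completers. No imputation, likelihood-based handling or sensitivity analysis for a missing T2 is stated.

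**The concern.** There are two separate faults.

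**The label.** In a single-arm study, intent-to-treat can reasonably mean that patients are analysed whether or not they exercised. Nothing in J.2 removes a non-adherent patient who attends T2, so for those patients the label can hold. It cannot hold for a patient without T2, because a paired test has no difference to use.

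**The inference.** J.3 gives two reasons for expecting no substantial bias. Minimal dropout is a valid kind of reason, although the same sentence expects 15%. Sample-size inflation is not a reason. It replaces the number of pairs lost, not the patients lost. Comparing baseline characteristics may show who dropped out, but it corrects nothing.

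Section B and H.1 intend the effect sizes, means and SDs for planning a larger trial. As written, a both-visits estimate would be passed on under an intent-to-treat name, with an invalid reason for trusting it.

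**Working it through.** **Inputs.** From H.1: 40 enrolled, 15% attrition, at least 34 completers, a 0.5 SD design effect, a 2-point meaningful change, TNS-PV mean 3.36 (pilot baseline), SD 3.66 at both visits, correlation 0.4, type I error 0.05. H.1 states a two-sided test for the other outcomes; I assume the same for TNS-PV. From F.1: entry requires TNS-PV of 3 or more.

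**Step 1: the plan's own figures.** 40 × 0.85 = 34 pairs; 40 × 0.15 = 6 without T2. Paired t-test power (noncentral t) at 0.5 SD of change:

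| Pairs | Power |
|---|---|
| 33 | 79.5% |
| 34 | 80.8% |
| 40 | 86.9% |

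For the 2-point scenario, SD of change = 3.66 × √(2 × (1 − 0.4)) = 4.01, and 2/4.01 = 0.499 gives 80.6% at 34 pairs. H.1 is reproduced: 34 is the smallest number reaching 80%, and inflation to 40 is what delivers it.

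**Step 2: bias of the both-visits mean.** With a fraction m missing, the all-enrolled mean change is (1 − m) × completers + m × dropouts. So

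bias = m × (completer mean change − dropout mean change).

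With m = 0.15, each 1-point difference moves the estimate by 0.15 points. N does not appear in the formula. As a check, a simulation with a 2-point difference gave a bias of about 0.3 points whether N was 34, 40, 47 or 400. Only the standard error fell, from 0.73 at 34 to 0.22 at 400.

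**Step 3: how large it might be.** The documents do not say how dropouts would differ, so this step rests on assumptions: bivariate normal scores with the H.1 inputs, entry at T1 ≥ 3, no intervention effect, 15% dropout, and a logistic dropout slope of 0.5, 1 or 1.5 log-odds per SD. Change is T2 minus T1, so a positive bias understates improvement and a negative one overstates it.

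| Dropout depends on | Slope 0.5 | Slope 1 | Slope 1.5 |
|---|---|---|---|
| T1 | +0.12 | +0.22 | +0.29 |
| T2 | −0.21 | −0.38 | −0.50 |
| Change | −0.26 | −0.47 | −0.62 |

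Slope 1 on T1: completers −1.40, dropouts −2.86; 0.15 × 1.46 = +0.22. Slope 1 on T2: completers −1.99, dropouts +0.53; 0.15 × (−2.52) = −0.38. Flooring scores at 0 and rounding them gives +0.12 to +0.32, −0.20 to −0.49 and −0.25 to −0.62. A separate run put the largest change-related value at −0.63.

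**Step 4: scale.** The standard error with 34 pairs is about 0.6 points in the simulated entrants (0.62 normal, 0.59 floored). From the untruncated H.1 inputs it is 4.01/√34 = 0.69. Only the strongest change-related case reaches or slightly exceeds 0.6. The nominal 95% paired interval covers the all-enrolled change 92% to 95% of the time for T1-related dropout and 86% to 94% for T2-related dropout. I leave the biases in points, because J.2 standardises by a pooled SD that the documents do not give for patients selected at T1 ≥ 3.

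**Step 5: what a likelihood fit would do.** At slope 1, fitting to everyone with T1 takes the T1-related bias from +0.22 to 0.00. For T2-related dropout it goes from −0.38 to −0.43, slightly worse. Root mean squared error, both-visits estimate against likelihood, is 0.65 and 0.63 (T1-related), 0.70 and 0.73 (T2-related), and 0.62 and 0.61 (random dropout).

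**The case against.** The strongest reply is that J.3 denies only substantial bias, and most of the figures above are below one standard error. They come from assumed slopes, and 6 missing is a planning allowance, since H.1 expects at least 34 completers. This stands. A reader might infer that J.3's conclusion is wrong, or that the Aim 2 estimate will be materially biased. The documents support neither: they say nothing about how dropouts differ, so neither size nor direction can be derived.

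A second reply is that the repeated measures ANOVA already solves the problem. A reader might equally infer that it drops the same patients. Neither follows. A classical ANOVA with two visits needs complete pairs, whereas a likelihood fit would keep T1-only patients. The latter may be intended, since J.2 uses mixed models elsewhere, but the method is not stated.

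A third reply is that this is a feasibility study whose uncontrolled pre/post design limits the effect size more than missing T2 does. That is fair on proportion. In the simulation, selection at T1 ≥ 3 alone produces a change of −1.6 points (−1.3 floored) without any intervention effect, though that figure depends on the model. It does not make the label or the inflation argument correct.

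**Conclusion.** The point holds, at modest size. The plan claims a property that its paired tests lack for patients without T2, and one of J.3's two reasons supports power, not freedom from bias. The label may stand for non-adherent patients who attend T2, and a reader should not take the finding to reach them. Minimal dropout remains a legitimate premise, so it would also be wrong to say that J.3 rests on inflation alone.

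The certain parts are the count (up to about 6 of 40), the power (80.8% at 34 pairs) and the bias formula, which is free of N. The point values rest on assumed dropout slopes and normal or floored scores. They are illustrations, not bounds. The effect is confined to the Aim 2 estimates and their intervals; Aim 1 is unaffected. The plan should be changed because the correction is cheap, not because a large bias has been shown.

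**What to change.** 1. **J.3:** limit the inflation statement to power.
2. **J.2:** label paired t-test and signed-rank results, biomarkers included, as analyses of patients with both visits, and give the number of pairs for each outcome.
3. **J.2:** fit the already planned age- and activity-adjusted repeated-measures model by maximum likelihood to all enrolled patients with T1, regardless of adherence (both visits as outcomes, unstructured covariance). State the missing-at-random assumption. Report this as the intent-to-treat estimate beside the paired result.
4. **TNS-PV only:** add a sensitivity analysis that shifts missing T2 values in both directions from the model's prediction, for example by the plan's own 2-point meaningful change. With 6 of 40 missing this moves the estimate by 6/40 × 2 = 0.30 points either way. Outcomes on other scales would need their own shifts.

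The cost is SAP wording and a few lines of code, with no new patients or visits. The drawback of item 3 is that it removes T1-related bias but gains little overall, and is slightly worse than the both-visits estimate if dropout depends on T2. That is why the paired result should stay beside it and item 4 should accompany it.
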